5.5.3.1 Serious Events Reporting Criteria

Serious AEs must be reported to the Sponsor or Sponsor representative within 24 hours of the Investigator's knowledge of the event. An SAE report form, including at minimum subject identification, AE description, and onset date must be forwarded to the Sponsor or Sponsor representative at the following number/email:

Email: [contact]
SAE [contact]

Upon availability of any new information, the subject's medical records and CRFs must be updated, and the information is to be provided to the Sponsor when applicable.

5.5.4 Additional Safety Assessments

Refer to the MOP for a description of the following procedures to be performed in the study.

5.5.4.1 Best Corrected Visual Acuity

BCVA will be measured in both eyes starting at Screening (Day -14 to Day -1) and at all attended visits, using an ETDRS chart, with the use of standardized manifest refraction and testing protocol as described in the Manual of Procedure. BCVA evaluation should precede any

study procedure that requires contact with the eye. All examiners must be certified prior to the Screening visit.

5.5.4.2 Intraocular Pressure

IOP will be measured in each eye at Screening (Day -14 to Day -1), before and after injection at Baseline (Day 0), and at all other attended visits prior to pupil dilation. The same type of tonometer should be used throughout the study for the same subject. At the Baseline visit, tonometry will be performed prior to administration of AXT107 and will be repeated at 30 (\pm 10) minutes post-injection of AXT107. Elevated IOP of \geq 30 mmHg will be re-measured at 60 (\pm 10) minutes post injection of AXT107.

5.5.4.3 Slit Lamp Biomicroscopy

Slit lamp biomicroscopy will be performed on each eye starting at Screening (Day -14 to Day -1) and at all attended visits. Assessment of the eyelids, conjunctiva, cornea, anterior chamber, iris, and lens will be documented. At the Baseline visit, the biomicroscopy examination will be performed prior to administration of AXT107.

5.5.4.4 Dilated Fundus Examination

DFE will be performed on each eye at Screening (Day -14 to Day -1), before and after study drug injection at Baseline (Day 0), and at all other attended visits to assess change from baseline and the visibility of AXT107. Assessments of the vitreous, retina, macula, choroid, optic nerve, and cup/disc ratio will be documented. Additional follow-up visits may be required to evaluate the AXT107 visibility if AXT107 is still visible at Visit 15/Exit (Week 48).

5.5.4.5 Spectral Domain Optical Coherence Tomography

SD-OCT images will be captured for each eye starting at Screening (Day -14 to Day -1) and at all attended visits, following the standardized procedures detailed in the Reading Center Manual. The approved equipment is also listed in the Reading Center Manual.

5.5.4.6 Fundus Photography

Fundus photography of each eye is to be obtained at Screening (Day -14 to Day -1), Visit 6 (Week 12), Visit 9 (Week 24), and Visit 15/Exit (Week 48). Refer to the Reading Center Manual for the procedure to obtain color FP.

5.5.4.7 Fluorescein Angiography

Fluorescein angiography of each eye will be obtained at Screening (Day -14 to Day -1), Visit 6 (Week 12), Visit 9 (Week 24) and Visit 15/Exit (Week 48). Sodium fluorescein will be injected into systemic circulation and digital images of the retina will be taken with blue light illumination at 490 nm of wavelength. Refer to the Reading Center Manual for the procedure.

5.5.4.8 Optical Coherence Tomography Angiography

OCT-A images will be captured at selected sites only. Images will be taken for each eye starting at Screening (Day -14 to Day -1) and at all attended visits, and will follow standardized procedures as detailed in the Reading Center Manual.

5.5.4.9 Widefield Retinal Imaging (Optos)

Widefield retinal image will be used to capture the AXT107 visibility in the study eye at Baseline (Day 0) after AXT107 injection, Week 8, and Week 36 at selected sites.

5.5.4.10 AC Tap

Anterior chamber paracentesis will be performed at selected sites at Baseline (Day 0), Visit 4 (Week 4), Visit 6 (Week 12), Visit 9 (Week 24), and Visit 14 (Week 44).

5.5.4.11 Optical Coherence Tomography Imaging at Home

Home OCT imaging will be performed weekly for each eye using the Notal Vision Home OCT device by study subjects, after enrollment at selected sites.

5.5.4.12 Visual Acuity Measurement at Home

Visual acuity measurement will be performed weekly for each eye, utilizing the M&S Technology visual acuity system at home by study subjects, after enrollment at selected sites.

5.5.4.13 Laboratory Evaluation

Laboratory tests (fasting for diabetic subjects) will include a complete blood count (hematology and differential), chemistry panel, and urinalysis at Screening (Day -14 to Day -1), Visit 9 (Week 24), and Visit 15 (Week 48). The Screening clinical laboratory results must be reviewed prior to enrollment to identify any clinically significant disease that in the opinion of the Investigator may preclude the subject from participation in the study. An anti-drug antibody (ADA) assay will be completed at Screening, Visit 4 (Week 4), Visit 6 (Week 12), and Visit 15 (Week 48/Exit).

5.5.4.14 Vital Signs

Heart rate and blood pressure will be measured starting at Screening (Day -14 to Day -1) and at all attended visits, using an automated or manual blood pressure monitor. Systolic and diastolic blood pressures will be recorded in millimeters of mercury (mmHg), and heart rate will be recorded in beats per minute (bpm).

5.5.4.15 Physical Examination

A complete physical examination will be conducted by the Principal Investigator or designee at Screening (Day -14 to Day -1).

5.5.4.16 Pregnancy

Women of childbearing potential are not excluded from the study as long as it can be determined at Baseline that they are not pregnant, nursing, or planning a pregnancy, and are using effective methods of contraception. Effective contraception methods include:

- Total abstinence (when this is in line with the preferred and usual lifestyle of the subject). Periodic abstinence (e.g., calendar, ovulation, symptothermal, post-ovulation methods) and withdrawal are not acceptable methods of contraception
- Female sterilization (have had surgical bilateral oophorectomy with or without hysterectomy) or tubal ligation at least 6 weeks before Baseline. In case of oophorectomy alone, only when

- the reproductive status of the woman has been confirmed by follow up hormone level assessment
- Male sterilization (at least 6 months prior to Baseline). For female subjects in the study, the vasectomized male partner should be the sole partner for that subject
 - Barrier methods of contraception: condom or occlusive cap (diaphragm or cervical/vault caps) with spermicidal foam/gel/film/cream/vaginal suppository
 - Use of oral, injected or implanted hormonal methods of contraception or other forms of hormonal contraception that have comparable efficacy (failure rate < 1%), for example hormone vaginal ring or transdermal hormone contraception
 - Placement of an intrauterine device (IUD) or intrauterine system (IUS)

Pregnancy is not considered an AE, but must be reported if occurred during a clinical study. Female subjects must be instructed to contact the Investigator immediately if pregnancy is suspected during their participation in the study. Every attempt will be made to collect data on the pregnancy of female subjects and/or pregnant partners of male subjects. Decision regarding continuation of the subject in the study will be made based upon the circumstances surrounding the pregnancy. Pregnancy must be followed to term to assess for potential complications. Complications may be reportable based on clinical judgement.

5.6 Assessment of Efficacy

5.6.1 Central Subfield Thickness

SD-OCT will be performed for both eyes starting at Screening (Day -14 to Day-1) and at all attended visits. Mean change in CST from Baseline (Day 0) will be assessed.

5.6.2 Best Corrected Visual Acuity

Mean change in ETDRS letters from Baseline (Day 0) and percentages improving at least 5, 10, and 15 letters will be assessed.

5.7 Contingency Measures in Case of a Global Emergency

In case of global or regional emergencies, such as the Covid-19 public health emergency, the investigational site may implement contingency plans to minimize the impact of the emergency on trial integrity and to reduce missing data, while ensuring the safety of study participants and the investigational site staff. In the event that study participants are unable or unwilling to attend in person study visits, telephone and virtual visits may be conducted for completion of assessments that can be conducted without requiring an in-person evaluation by the study investigator (eg, in-home assessments of OCT and VA, subject reported symptomology and AEs). Virtual or telephone visits should be clearly documented as such in the case report forms to account for missing safety and efficacy assessment when summarized.

Deviations from the protocol may be unavoidable during the current Covid-19 public health emergency. Delayed or missed visits due COVID-19 illness and/or COVID-19 control measures should be documented as such in an effort to assess the potential impact of Covid-19 on study conduct and the collection of data.

6. STATISTICAL ANALYSIS PLAN

6.1 Analysis Populations

Intent-to-Treat (ITT) Population:

The ITT population will include all subjects who have received study medication. This population will be the primary population for efficacy analyses and will be used to summarize all efficacy variables.

Safety Population:

The safety population will include all subjects who have received study medication. This population will be used to summarize safety variables and will summarize subjects as treated.

6.2 Statistical Hypotheses

No statistical hypotheses are defined for this study.

6.3 Statistical Methods

Age, sex, race, ethnicity, and baseline assessments will be summarized and listed by dose level. Medical history, history of ocular surgery and procedures, and concomitant medication will also be summarized and listed.

Changes from baseline in BCVA and retinal thickness (CST) will be summarized by dose level using continuous summary statistics. BCVA change will be summarized using categorical summaries as well, including frequency counts and percentages improving at least 5, 10, and 15 letters.

Verbatim descriptions of AEs will be mapped to MedDRA thesaurus terms and be presented in a data listing. Treatment emergent AEs, those that occur after the first dose of study medication, will be summarized by dose level using frequency and percent for each system organ class (SOC) and preferred term (PT) within each SOC. Summaries will be presented separately for ocular and non-ocular AEs. TEAEs will be summarized by severity and study drug relatedness.

BCVA will be summarized at each time point using both continuous summaries (ETDRS letter score), including change from Baseline (Day 0), and categorical summaries, including change from Baseline (Day 0) on an ETDRS chart in the number of lines.

IOP will be summarized at each time point using both continuous summaries, including change from Baseline (Day 0), and categorical summaries for pre-stated categories of change in IOP.

Slit lamp biomicroscopy and ophthalmoscopy measures will be summarized at each measured time point using categorical summary statistics.

FA will be summarized by visit.

DRSS will be summarized by visit and change from Baseline (Day 0) to each visit.

Vital signs will be summarized at each visit and for change from Baseline (Day 0) to each visit using continuous summary statistics by treatment group and visit.

Clinical laboratory results will be summarized using both continuous summaries, including change from Baseline (Day 0), and discrete summaries, including frequency and percent of subjects with an abnormal value and shift tables from Baseline (Day 0). Additionally, laboratory data will be presented in data listings.

Exploratory analyses will be performed to summarize the results obtained from the Notal Vision Home OCT device and home M&S® Technology visual acuity measurement.

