
- Any other serious ocular or systemic adverse event (AE) that, in the opinion of the Investigator, is related to the study drug in ≥ 1 subject

Rescue therapy with the Investigator's preferred treatment will be allowed starting at Week 12 for any subject who has received injection of AXT107 and for whom there is ≥ 7 letter ETDRS BCVA decrease from Baseline (Day 0) or ≥ 75 μ m increase in Central Subfield thickness (CST) compared to the lowest previous visit.

Number of Subjects:

Approximately 18 subjects with diabetic macular edema secondary to type 1 or type 2 diabetes mellitus will be enrolled. The final number of subjects enrolled may be adjusted based on the presence of dose limiting toxicities.

Duration of the Study:

The expected duration of this clinical study is up to 50 weeks, including a 14-day screening phase and 48 weeks of on treatment/ follow up phase.

Inclusion and Exclusion Criteria:

Inclusion Criteria:

1. 18 years of age or older
2. Type 1 or 2 diabetes mellitus with center-involved DME and with central subfield thickness ≥ 305 μ m (females) or 320 μ m (males) on Spectralis® Spectral Domain Optical Coherence Tomography (SD-OCT) device or 290 μ m (females) or 305 μ m (males) on Cirrus® SD-OCT device and with intraretinal or subretinal fluid as evidenced by Spectral Domain Optical Coherence Tomography (SD-OCT) in the study eye at Screening, as confirmed by the Investigator
3. BCVA in the study eye at Baseline (Day 0) between 65 and 23 ETDRS letters (20/40 and 20/320 Snellen equivalent) with BCVA decrement determined by the Investigator primarily attributable to DME
4. BCVA of 34 ETDRS letters or better (20/200 or better Snellen equivalent) in the non-study eye at Baseline (Day 0)
5. Able and willing to give signed informed consent and follow study instructions

Exclusion Criteria:

1. Any signs of high risk proliferative diabetic retinopathy in the study eye and related complications, as determined by the Investigator
2. Previously treated patients who are non-responders to anti-VEGF determined by the Investigator
3. Panretinal photocoagulation within 6 months or macular laser photocoagulation within 3 months from Screening in the study eye
4. Use of intraocular or periocular corticosteroids within 4 months (with the exception of fluocinolone acetonide intravitreal implant which is excluded), Aflibercept within 8 weeks, Ranibizumab and Bevacizumab within 6 weeks from Baseline (Day 0) in the study eye

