5.3.3 Rescue Therapy

Rescue therapy with the Investigator's preferred treatment will be allowed starting at Week 12, for any subject who has received injection of AXT107 and for whom there is ≥ 7 letter ETDRS BCVA decrease from Baseline (Day 0) or $\geq 75 \mu\text{m}$ increase in CST compared to the lowest measurement at any previous visit. It is recommended that rescued subjects complete all study follow up visits through Week 48/Exit.

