5.3.4 Concomitant Medication

There are no prohibited concomitant medications in the study. When possible, concomitant medications should be used with a consistent dose throughout the study. The use of concomitant medications (prescription or over-the-counter) will be recorded in the source documents during the study, using the generic name, indication, route of administration, frequency, dose, start date and stop date (if applicable).

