6.5 Handling of Missing Data

For safety measures, missing scores will not be imputed for data summaries. Completely or partially missing onset and resolution dates for AEs and completely or partially missing start and end dates of concomitant medications will be imputed in a conservative fashion. For bioactivity endpoints, missing post-treatment values will be imputed using the last-observation-carried-forward (LOCF) approach.

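### Section 6 has no rule for CST and BCVA values measured after rescue, so if rescue works, the late by-dose summaries can make one AXT107 injection look longer-acting than it is

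*Combined protocol and SAP*

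**What the plan says.** Section 5.3.3 opens rescue at Week 12 for a loss of at least 7 ETDRS letters from Baseline or a CST rise of at least 75 µm. The rise is an "increase in CST compared to the lowest measurement at any previous visit"; the synopsis has "increase in Central Subfield thickness (CST) compared to the lowest previous visit". Staying in the study after rescue is advised, not required: "It is recommended that rescued subjects complete all study follow up visits through Week 48/Exit".

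The analysis text does not take this up:

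- Section 6.1 defines the ITT population as all dosed subjects and adds: "This population will be the primary population for efficacy analyses and will be used to summarize all efficacy variables".
- Section 6.3: "Changes from baseline in BCVA and retinal thickness (CST) will be summarized by dose level using continuous summary statistics". It also plans the proportions gaining at least 5, 10 and 15 letters. It names each time point for BCVA but none for CST. Section 5.6.1 has SD-OCT at all attended visits and adds: "Mean change in CST from Baseline (Day 0) will be assessed".
- Section 6.5: "For bioactivity endpoints, missing post-treatment values will be imputed using the last-observation-carried-forward (LOCF) approach".
- Section 6.6 plans interim looks at Weeks 12, 24 and 36.

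No part of section 6 mentions rescue: there is no exclusion, flag, composite rule, count of rescues or time to rescue. Section 5.3.4 states "There are no prohibited concomitant medications in the study" and has medications recorded with indication and dates. Section 6.3 summarises and lists them.

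**The concern.** Section 4 makes duration of action part of the secondary objective, and there is no control arm. The by-dose CST and BCVA summaries at later visits are therefore the main planned evidence on how long one injection lasts, although FA, DRSS and the home measurements are also summarised (also without a rescue rule).

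Rescue is triggered by worsening, so subjects whose AXT107 effect has faded are the ones most likely to receive another treatment. If that treatment works, their later values show its effect but are averaged under an AXT107 dose label. A short-acting dose can then look durable, and doses with different rescue rates can look alike. LOCF does not close the gap, because a value observed after rescue is not missing. If a rescued subject leaves after a post-rescue visit, LOCF as written carries the post-rescue value on to Week 48.

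**Working it through.** **Plan's own figure.** Section 6.4: 3 doses × 6 subjects = 18, which agrees. The plan gives no alpha, effect size or SD, so there is no power figure to reproduce.

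**Visits exposed.** In-clinic post-baseline visits are Weeks 1, 4, 8, 12, 16, 20, 24, 28, 32, 36, 40, 44 and 48, which is 13. Rescue opens at Week 12, so if that visit's measurements precede rescue, the first post-rescue measurement is Week 16. Weeks 16 to 48 give 9 visits. Two of the three interim looks (Weeks 24 and 36) fall among them; Week 12 is essentially unaffected.

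**Arithmetic from the documents' figures.** The shift in a dose-group mean is k × f × trigger / 6, where k is the number rescued and f is the share of the worsening that rescue reverses. The documents give neither, so both are assumptions.

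- CST, k = 1: 75/6 = 12.5 µm if f = 1; 6.25 µm if f = 0.5; 0 if f = 0.
- BCVA, k = 1, f = 1: 7/6 = 1.17 letters.
- Responder proportions: 100/6 = 16.7 points per changed subject.

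Example with assumed values: all 6 subjects reach -100 µm, then 3 rebound by 75 µm and are rescued. Holding the rescue-day value gives (3 × (-25) + 3 × (-100))/6 = -62.5 µm. Observed values after full reversal give -100 µm, as if the injection were still fully active.

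**Illustration by simulation.** Every input is assumed except the visit schedule and the CST trigger: mean peak reduction 75 µm (between-subject SD 30, floored at 0), noise SD 10 µm at every visit including baseline, every eligible subject rescued, and CST set to a fixed level after rescue. Only the CST trigger is applied; BCVA is not simulated. There are 200,000 subjects per scenario. The true Week 48 change under AXT107 alone is 0 in both.

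| Loss of effect | Rescued | Week 48 mean, rescue level -50 µm | Rescue level -100 µm |
|---|---|---|---|
| Full to Week 12, gone by Week 24 | 78% | -38 | -77 |
| Full to Week 12, linear to 0 at Week 48 | 67% | -29 | -57 |

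If rescue only returns CST to baseline, so has no effect of its own, the fast-loss Week 48 mean is 0. For a single group of 6 with fast loss and level -50, the 5th to 95th percentile of the mean is -54 to -20 µm.

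**The interim looks depend on speed of loss.** With slow loss, the Week 24 mean is -50 µm against a truth of -50, so there is no bias. The Week 36 mean is about -27 µm (level -50) or -34 µm (level -100) against a truth of -25: off by about 2 or 9 µm.

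**The direction can reverse.** With slow loss, peak 200 µm and level -50, the Week 36 as-observed mean is about -50 µm against a truth of -66.7 (200 × 12/36), which understates the effect.

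**Limits of the alternatives.** Carrying the last pre-rescue value forward gives a Week 48 mean, against a truth of 0, of -5 µm at peak 75 and -103 µm at peak 200 (fast loss), or -12 and -120 µm (slow loss). Time to rescue depends on peak as well as duration. Without noise and with slow loss, a subject whose lowest value is -150 first qualifies at Week 32 (-150 × 16/36 = -66.7, a rise of 83.3). One whose lowest value is -200 qualifies at Week 28 (-200 × 20/36 = -111, a rise of 89).

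**The case against.** The strongest reply is that this is a first-in-human, descriptive study with a safety primary objective, no hypotheses and a sample size with no statistical basis. Summarising all dosed subjects as observed is a legitimate choice, and with 6 per dose a reader can set individual courses beside the medication listing. Drug rescue is largely recoverable, since Table I-1 collects concomitant medications at every in-clinic visit and section 5.3.4 asks for indication and dates.

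Much of this stands. It limits the stakes and means no new record is needed for drug rescue. It does not remove the gap. The plan never says it has chosen the as-observed summary, that summary does not isolate the duration of one injection, and a listing leaves the planned means and proportions unchanged. Section 5.3.4 also does not clearly cover a procedure such as laser.

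Three stronger readings are tempting, and the documents do not support them:

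- A reader might infer that the plan's duration estimate is biased. The plan names no duration endpoint; the risk lies in how late means and proportions are read.
- A reader might infer that the Week 24 and Week 36 looks must be distorted, or that distortion always favours AXT107. Both depend on inputs the documents do not give, as the slow-loss and large-peak cases show.
- A reader might infer that time to rescue should become the main measure of duration. Because the CST trigger is a rise from the lowest value, a more active dose can be rescued sooner at the same true duration.

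**Conclusion.** The omission is certain from the text: sections 6.1, 6.3 and 6.5, followed exactly, can place rescue effect under an AXT107 dose label from Week 16 on. It should be fixed, because duration is a stated objective without a control arm and the remedy is cheap.

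Its size is not certain. The robust figures are 12.5 µm and 16.7 percentage points per affected subject, given 6 per dose and rescue that fully reverses the trigger rise or changes a responder's status. The Week 48 shifts of -38 and -29 µm illustrate what assumed inputs produce and do not predict this trial. There is no distortion if nobody is rescued, and little or no overstatement if rescue does not work. Type I error and power are not at issue.

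**What to change.** Amend sections 6.3 and 6.5 and the synopsis, leaving rescue criteria, visits and sample size unchanged:

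1. Record the date and type of any study-eye DME treatment after Day 0. Drug rescue is already captured as concomitant medication; add a CRF entry for procedures such as laser.
2. Report by dose the number rescued by each visit and the time to first rescue, with the criterion met and each rescued subject's lowest and rescue-day CST. State that these are read beside the means and are not a stand-alone measure of duration.
3. In the 5-, 10- and 15-letter proportions, count a subject as a non-responder at visits after rescue, and show the as-observed proportions alongside.
4. Show by-dose CST and BCVA means as observed and, as a sensitivity display, with post-rescue values set aside and the last pre-rescue value carried forward. Keep rescued subjects in both. State that LOCF never carries a post-rescue value in the second display, that this display can still overstate duration when the peak is large, and that neither set is an unbiased estimate of AXT107 alone.
5. Use the same displays at the Week 24 and Week 36 looks, and fix the rule before the first of them, since in an open-label study a rule chosen later could be driven by the data.

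The cost is some wording, one CRF entry, a few table rows, and two sets of means that must be read together.

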5.1.4 Criteria for Termination of the Study (Stopping Rules)

The DMC will conduct ongoing reviews of collected safety data to determine the need for early termination of the study. Stopping rules will be incorporated if any of the following events are identified:

- Decrease in Early Treatment Diabetic Retinopathy Study (ETDRS) best corrected visual acuity (BCVA) of ≥ 15 letters (3-line decrease) unrelated to the natural progression of the disease and determined by the Investigator to be related to the study drug in ≥ 2 subjects
- Intraocular inflammation (anterior or posterior) grade +2 or more in ≥ 2 subjects (using SUN Grading Working Group and Nussenblatt et al grading)
- Increase in intraocular pressure (IOP) to ≥ 30 mmHg for more than 24 hours post-injection in ≥ 2 subjects despite IOP lowering medication treatment
- Any other serious ocular or systemic adverse event (AE) that, in the opinion of the Investigator, is related to the study drug in ≥ 1 subject

Upon DMC's recommendation for study termination, further enrollment of study subjects in the study will be discontinued. Subject withdrawal procedures must be followed for all active subjects to ensure the safety of the subjects at the conclusion of the study.

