Severe: Considerable interference with the subject's daily activities; medical intervention/therapy required

The Investigator must also make a determination of relatedness to the study drug (related or not related), based on the Investigator's clinical judgment, facts (product information or Investigator's Brochure), evidence, and scientific rationales as to whether there is a causal relationship between the AE and AXT107.

- An AE must be reported as **Related** to AXT107 if there is a reasonable possibility that the experience may have been caused by AXT107, and the AE cannot be readily explained by the subject's clinical state, concurrent illness, or concomitant therapies.
- An AE may be considered as **Not Related** to AXT107 if evidence that the AE has an etiology other than the AXT107 (e.g., pre-existing medical condition, underlying disease, concurrent illness, or concomitant medication); and/or the AE has no plausible temporal relationship to administration of the AXT107 (e.g., newly diagnosed condition after administration of AXT107).

The Investigator will be required to assess the outcome of the AE as one of the following:

- Resolved
- Resolved with sequelae
- Resolving
- Not Resolved
- Fatal
- Unknown

An event that is assessed as resolved with sequelae or resolving indicates that the subject has stabilized to a level acceptable to the Investigator and has concurrence by the Sponsor.

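### The safety summaries in Section 6.3 have no flag or split at rescue, so effects of a rescue treatment can be counted under the AXT107 dose level

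*Combined protocol and SAP*

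**What the plan says.** **Analysis (Section 6.3).** The adverse event tables are defined by: "Treatment emergent AEs, those that occur after the first dose of study medication, will be summarized by dose level". The same section adds that "TEAEs will be summarized by severity and study drug relatedness". For the eye measures, "IOP will be summarized at each time point using both continuous summaries, including change from Baseline (Day 0), and categorical summaries". Slit lamp and ophthalmoscopy findings, FA and DRSS are also summarised by visit; the synopsis limits DRSS to visits at which it is measured. Neither these paragraphs, nor the populations in Section 6.1, nor the missing-data rules in Section 6.5 mention rescue.

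**Rescue (Section 5.3.3).** "Rescue therapy with the Investigator's preferred treatment will be allowed starting at Week 12", subject to a BCVA or CST criterion. Afterwards, "It is recommended that rescued subjects complete all study follow up visits through Week 48/Exit".

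**Causality (Section 5.5.2).** An event is Related only if, among other things, "the AE cannot be readily explained by the subject's clinical state, concurrent illness, or concomitant therapies". It may be Not Related if there is evidence of another cause ("e.g., pre-existing medical condition, underlying disease, concurrent illness, or concomitant medication").

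**Stopping criteria (Section 5.1.4 and synopsis).** The BCVA criterion and the criterion for other serious events require the investigator to judge the event related to study drug. The inflammation criterion reads "Intraocular inflammation (anterior or posterior) grade +2 or more in ≥ 2 subjects", with no such condition. The IOP criterion has none either, but it is tied to a post-injection period without naming the injection.

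**The concern.** Safety and tolerability is the primary objective, and there is no control arm. The dose-level tables are the main evidence, and each column has about 6 subjects. From Week 12 a column can contain eyes that have also received a different active treatment. If one dose is rescued more often than another, its adverse event, IOP and inflammation results can look worse, or its FA and DRSS results better, for reasons unrelated to AXT107. A reader of the planned tables could not tell.

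The documents treat such exposure as important elsewhere. The exclusion criteria impose washout periods before Baseline for ocular corticosteroids, aflibercept, ranibizumab and bevacizumab. Section 3.4 lists endophthalmitis, vitreous hemorrhage and retinal detachment as risks of intravitreal injection as such. The analysis has no matching provision when such treatments are given after Week 12.

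The outputs affected are the final tables, the Week 24 and Week 36 interim analyses (Section 6.6), the DMC's ongoing reviews, and any later decision on a dose up to 1.0 mg that draws on post-rescue data.

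**Working it through.** **No design figure to reproduce.** Section 6.2 defines no hypotheses, and Section 6.4 says the sample size has no statistical basis. The counts agree: 3 doses × 6 = 18 = 9 + 9.

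**Which planned outputs separate rescue effects?**

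| Output (Section 6.3) | Runs past rescue | Separates rescue effects |
|---|---|---|
| TEAEs by SOC, PT and dose | Yes | No |
| TEAEs by relatedness | Yes | Partly, by unmasked judgement |
| IOP, slit lamp, ophthalmoscopy | Yes | No, unless the change is also reported as an AE |
| FA, DRSS | Yes, where measured | No |

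**Time exposed.** Rescue can start at Week 12 of 48: (48 − 12)/48 = 36/48 = 75%. This is a ceiling, reached only by a subject rescued at Week 12.

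**Visits exposed.** On-site visits after injection are Weeks 1, 4, 8 and 12, then every 4 weeks to 48, which makes 13. I take the Week 12 measurements as preceding any rescue, because BCVA and CST decide it. That leaves Weeks 16 to 48, or 9 of 13; counting Week 12 gives 10 of 13. This fraction does not apply to FA. FA is done at Screening and Weeks 12, 24 and 48 (Section 5.5.4.7), so 2 of its 3 post-injection assessments can follow rescue.

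**Effect of one event.** 1/6 = 16.7 percentage points in a dose column.

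**Illustration of likelihood (assumed inputs).** The documents give neither the share rescued nor the event rate. Let p be the chance of a rescue-caused event per rescued subject, taken as independent between subjects.

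At least one event in a dose group with 3 of 6 rescued is 1 − (1 − p)³. This gives 0.0297 at p = 1%, 0.1426 at 5% and 0.2710 at 10%.

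For rescue alone to reach the two-subject count in the inflammation criterion with m rescued subjects, P = 1 − (1 − p)^m − m·p·(1 − p)^(m − 1):

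| m rescued of 18 | p = 1% | p = 5% | p = 10% |
|---|---|---|---|
| 6 | 0.0015 | 0.0328 | 0.1143 |
| 9 | 0.0034 | 0.0712 | 0.2252 |
| 12 | 0.0062 | 0.1184 | 0.3410 |
| 18 | 0.0138 | 0.2265 | 0.5497 |

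The answer depends almost entirely on the assumptions. The table shows only that the chance can be negligible or substantial, and that the documents cannot say which.

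**The case against.** **Relatedness is already tabulated.** A reader might infer that rescue harms will be reported as AXT107 toxicity. The documents do not support that. An all-causality TEAE table is not an attribution, and the Section 5.5.2 definitions give a rescue reaction a route to Not Related. Section 5.5.2 also has clinically significant changes from baseline evaluated as AEs, so some IOP and slit lamp findings enter that process. This stands as mitigation. It does not change the IOP, slit lamp, FA and DRSS tables themselves. It can also err the other way: a late AXT107 effect after rescue may be put down to the rescue product.

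**Two open stopping criteria.** A reader might infer that both the inflammation and IOP criteria count rescue events. Only the inflammation criterion is plainly open. Section 5.5.4.2 uses post-injection for the AXT107 injection, and the IOP criterion may mean the same; it is ambiguous rather than open. An attribution-free inflammation criterion may also be a deliberate precaution in a first-in-human study.

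**Contaminated stopping or escalation.** Neither follows. The synopsis makes the criteria a matter for DMC decision, so they are not automatic. The initial escalation reviews use 7-day data, well before rescue opens.

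**Pre-rescue data as the primary table.** This is tempting, but the documents argue against it. Rescue depends on worsening BCVA or CST, so the cut is outcome-dependent. AXT107 persisted in rabbit eyes for up to 12 months (Section 3.3), so real late harms would leave the main table.

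**Recoverable from listings.** With about 18 subjects, much could be reconstructed from the AE and medication listings. That is true, but an after-the-fact reconstruction is weaker than a planned summary.

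**Conclusion.** The point holds as a gap in the planned reporting. Followed as written, the by-dose safety, FA and DRSS summaries mix AXT107 effects with those of any rescue treatment, for up to 36 of 48 weeks in a rescued subject. One rescue-caused event shifts a dose-level rate by 16.7 percentage points, assuming 6 subjects per dose. How often this would happen is unknown. The size rests on a rescue share and event rate that the documents do not give, and the point would be empty if nobody were rescued.

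The stopping criteria are a narrower, separate matter of wording: Sections 5.1.4 and 5.3.3 and the synopsis do not say whether events after rescue count.

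**What to change.** - Keep the whole-study by-dose tables as planned.
- Add to Section 6.3 and the synopsis summaries of TEAEs, IOP, slit lamp and ophthalmoscopy, FA and DRSS, split into before and after first study-eye rescue.
- Flag rescue product and date in the listings and in DMC displays.
- Have the sponsor reconcile the inflammation and IOP stopping criteria (Section 5.1.4 and synopsis) with Section 5.3.3 on whether post-rescue events count. No stopping rule is proposed here.

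**Cost.** SAP and table-shell wording, a few more tables with small numbers, and one derived flag. Section 5.3.4 already records product, indication, route and start date for medications. Its list does not include the treated eye or non-drug procedures, so the sponsor should confirm that the CRF captures both for rescue. Late AXT107 effects in rescued subjects will fall in the post-rescue part, which is why the all-event tables must stay.
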